**Overview**

VTE associated harm is underappreciated among hospitalized patients and may be associated with missed doses of VTE prophylaxis medications. In order to ensure best practices, and administer a defect-free VTE prevention nurses must understand and educate patients on the importance of the VTE prophylaxis. We propose to conduct a randomized trial comparing the effect of a validated, real-time patient education bundle (PEB), to a program of nurse feedback and coaching (NFC) provided by nurse leaders.

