**Background**

Missed doses of prescribed Venous Thromboembolism (VTE) pharmacologic prophylaxis is significant problem. Data on patients admitted to The Johns Hopkins Hospital found approximately 12% of prescribed doses of pharmacologic VTE prophylaxis were not administered. There were several reasons for these missed doses. The leading reason (nearly 60% of missed doses) was patient or family member refusal for any reason.

Based on data collected by the Maryland Health Services Cost Review Commission (HSCRC) in the Maryland hospital-acquired conditions (MHAC) program, during 2011 half of patients who developed confirmed VTE at The Johns Hopkins Hospital were not administered one or more doses of prescribed VTE prophylaxis. These data indicate that missed or refused doses of VTE prophylaxis represent a significant and under-recognized contributor to sub-optimal VTE prophylaxis that will erode the beneficial impact of current efforts to improve rates of VTE prophylaxis ordering by physicians.

As part of a Patient-Centered Outcomes Research Institute (PCORI)-funded project, the investigators have developed a registry of missed doses of VTE prophylaxis that includes data on missed doses of VTE prophylaxis.

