## **Participants**

### **Eligibility Criteria**

Participating floors will be assigned one of two interventions based on a randomization sequence.

Eligible floors are defined as:

- A. All medical and surgical floors (non- intensive care units)
- B. 16 total floors (10 medicine, 6 surgery)

Eligible Patients are defined as: All patients on assigned floors except:

- A. Patient data for those transferred between floors will be excluded.
- B. Patient data for those on floors during the cross-over time will be excluded.

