## Nurse satisfaction

### **Analysis plan**

We will have a blinded biostatistician team perform all analyses.

We will use the intention-to-treat (ITT) approach.

We will compare outcomes across intervention periods.

We will compare outcomes based upon randomized floor.

We will use multiple outputation to reduce the levels of hierarchical structure to the floor and nurse level by randomly selecting one VTE prophylaxis dose per patient and reiterate the procedure 1000 times to bootstrap the p values for the comparisons. This methodology will be similar that taken previously in our prior work in similar circumstances.

We will adjust by floor type (medicine vs. surgery) and patient level characteristics (race, sex, age, insurance) when calculating proportions and risk of missed doses.

We will conduct a sensitivity analysis (excluding floors where prior intervention occurred).

Check for differential effect that may eliminate biases in pre-implementation data (by race, age, sex)

PRE-TRIAL (6 MONTHS)	PERIOD I (3 MONTHS)	PERIOD II (3 MONTHS)	POST-TRIAL (3 MONTHS)	
RANDOMIZATION	<pre> graph LR     A[RANDOMIZATION] --> B[PEB]     A --> C[NFC]     B --> D[NFC+PEB]     B --> E[PEB+NFC]     C --> D     C --> E     D --> F[POST-TRIAL PERIOD]     E --> F   </pre>	<pre> graph LR     A[RANDOMIZATION] --> B[PEB]     A --> C[NFC]     B --> D[NFC+PEB]     B --> E[PEB+NFC]     C --> D     C --> E     D --> F[POST-TRIAL PERIOD]     E --> F   </pre>	POST-TRIAL PERIOD	
Randomization with sequence generator	Block (Medicine): 5 Medicine floors- PEB 5 Medicine floors- NFC  Block (Surgery): 3 Surgery floors- PEB 3 Surgery floors- NFC	Block (Medicine): 5 Medicine floors- PEB+NFC 5 Medicine floors- NFC+PEB  Block (Surgery): 3 Surgery floors- PEB+NFC 3 Surgery floors- NFC+PEB	Observation assessment

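### Prior-intervention floors enter neither the randomisation blocks nor the listed covariates, so a chance imbalance can move the realised Period I PEB v NFC contrast; a prespecified floor flag would limit this cheaply

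*Combined protocol and SAP*

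**What the plan says.** Eligibility Criteria takes in all non-ICU medical and surgical floors, "16 total floors (10 medicine, 6 surgery"), and does not leave out floors with an earlier intervention.

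The design table at the end of the Analysis plan blocks the randomisation by floor type only. Period I has "5 Medicine floors- PEB 5 Medicine floors- NFC" in one block and "3 Surgery floors- PEB 3 Surgery floors- NFC" in the other, which makes 8 floors per arm. In Period II the medicine row reads "5 Medicine floors- PEB+NFC 5 Medicine floors- NFC+PEB", and the surgery row follows the same pattern, so every floor then has both interventions.

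On covariates the Analysis plan says: "We will adjust by floor type (medicine vs. surgery) and patient level characteristics (race, sex, age, insurance"). Prior intervention is not in that list, nor is a floor's own pre-trial missed-dose rate. The one place where the earlier intervention appears is the sensitivity analysis: "We will conduct a sensitivity analysis (excluding floors where prior intervention occurred"). The text does not say how many floors these are, which they are, what the earlier intervention was, when it took place, or whether its effect lasted.

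**The concern.** A planned exclusion implies that the team can identify the exposed floors and thinks exposure could matter to the result. Yet neither the allocation nor the main analysis uses it.

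A conventional crossover would cancel stable differences between floors, but this one does not do so for PEB alone v NFC alone. Period II has no single-intervention floors, so that contrast, which is secondary hypothesis 3, is made between floors in Period I. With 8 floors per arm, each surplus exposed floor moves an arm's mean by one eighth of whatever difference remains on exposed floors.

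The primary hypothesis, that both interventions reduce missed doses, leans on the pre-trial period. If exposed floors had already gained part of the benefit and had less left to gain, their change would be smaller and the average pre-post change would be diluted.

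**Working it through.** The plan gives no power calculation or effect size, so there is no figure of its own to reproduce. The floor counts agree: 10 + 6 = 16 and 5 + 3 = 8 per arm.

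**Inputs.** From the documents: 10 medicine floors split 5:5, 6 surgery floors split 3:3, and a background missed-dose rate ("approximately 12% of prescribed doses of pharmacologic VTE prophylaxis were not administered"). Assumed: 2 to 6 exposed floors in any medicine/surgery mix, and a missed-dose rate on exposed floors that is *e* = 2 to 4 percentage points lower (17% to 33% of 12%). If the earlier effect has decayed, *e* = 0.

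**Step 1: chance of an uneven split.** With *m* exposed medicine floors, the probability that *x* of them go to PEB is C(m,x)·C(10−m,5−x)/C(10,5). Surgery is the same with 6 and 3. The blocks are independent, and there are 252 × 20 = 5040 allocations.

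Example, 2 medicine + 2 surgery exposed:
- Medicine 1:1 has probability 2 × 70/252 = 0.556; 2:0 and 0:2 have 0.222 each.
- Surgery 1:1 has probability 2 × 6/20 = 0.600; 2:0 and 0:2 have 0.200 each.
- Even overall: 0.556 × 0.600 + 2 × 0.222 × 0.200 = 0.422.
- 4:0 either way: 2 × 0.222 × 0.200 = 0.089.
- 3:1 either way: 1 − 0.422 − 0.089 = 0.489.
- A difference of 2 or more: 0.489 + 0.089 = 0.578.

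Over every medicine/surgery mix:

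| Exposed floors | P(arms differ by 2 or more) |
|---|---|
| 2 | 40% to 50% |
| 3 | 10% to 22% |
| 4 | 40% to 58% |
| 5 | 0% (all surgery) to 30% |
| 6 | 50% to 62%; 0% if all 6 are surgery |

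With an odd count a difference of at least 1 floor is certain, and a difference of 2 or more means at least 3.

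**Step 2: shift in PEB v NFC if exposed floors stay lower in Period I.** With equal floor weights, shift = (difference in exposed floors/8) × *e*.
- 2 floors: 2/8 × 2 = 0.5 to 2/8 × 4 = 1.0 points.
- 4 floors: 4/8 × 2 = 1.0 to 4/8 × 4 = 2.0 points.
- *e* = 0: no shift.

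**Step 3: dilution of pre-post change if exposed floors start lower but end level with the others.** Dilution = (exposed floors/16) × *e*. With 4 exposed: 4/16 × 2 = 0.5 to 4/16 × 4 = 1.0 points.

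**Step 4: the two harms do not add.** Step 2 needs the gap to persist in Period I. A gap that persists in full lowers the before and after rates equally and leaves the change undiluted. Step 3 needs the gap to have closed, and then there is nothing left to shift PEB v NFC. A partly closed gap gives part of each.

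**The case against.** **Randomisation already deals with this.** In expectation it does. Blocked randomisation leaves PEB v NFC unbiased, and between-floor variation, prior exposure included, belongs in the standard error; the Analysis plan keeps the floor level in the analysis. A reader might infer that the contrast is biased by design. The documents do not support that. What stands is a matter of the realised allocation and of precision, and with 8 floors per arm it is not negligible.

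**The sensitivity analysis is sound.** Exposure precedes randomisation, so dropping those floors leaves a valid randomised comparison among the rest and removes the dilution. Unequal blocks cost precision, not validity, and keeping all floors in the main analysis fits the stated intention-to-treat approach. All of that stands. But the exclusion loses clusters (16 to 12 if 4 are exposed), leaves the headline estimate as it was, and comes with no rule for what to conclude if the two analyses disagree.

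**The six months of pre-trial data could absorb level differences.** They could under a within-floor change model, but the plan does not specify one and lists no baseline-rate covariate. Secondary hypothesis 6, on high v low performing floors, concerns a related but different factor.

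**The size is unknown.** This stands: every figure in points is conditional on assumed inputs, and zero is possible.

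**Conclusion.** The point holds as an efficiency and balance weakness in the main analysis. Prior exposure matters enough to the plan to justify an exclusion analysis, yet it is used in neither the blocks nor the listed covariates, and the design does not protect the Period I comparison from it. Under the assumed 2-4 point residual difference, a 2-floor imbalance would move PEB v NFC by 0.5-1.0 points against a background rate of about 12%. Alternatively, with 4 floors exposed and the gap closed by the end, the pre-post change would be diluted by 0.5-1.0 points.

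Three stronger readings should be avoided:
- That imbalance is likely whatever the number of exposed floors. For 2 to 6 floors, the chance of a difference of 2 or more runs from 0% to 62%, depending on the count and the mix.
- That both harms apply in full. They rest on opposite assumptions about whether the gap persists.
- That the earlier intervention was PEB. The Overview's phrase, "comparing the effect of a validated, real-time patient education bundle (PEB"), calls the bundle validated but does not say where it was used before, and the Analysis plan does not name the earlier intervention.

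The change is worth making because it is cheap, not because the trial's conclusions are shown to be unsafe.

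**What to change.** 1. State which floors had an earlier intervention, what it was and when. Define a yes/no flag per floor, which the sensitivity analysis already needs.
2. Add the flag as a prespecified floor-level covariate in the main PEB v NFC model, beside floor type.
3. For the pre-post contrasts, add flag-by-period, so that change is estimated separately in exposed and unexposed floors.
4. If randomisation has not been run, restrict it to allocations where exposed floors differ by at most one within each block **and** by at most one in total. The within-block limit alone is not enough: with 1 medicine + 1 surgery floor exposed, a 2-floor difference would still occur half the time. The restriction leaves ample choice. With 4 medicine + 2 surgery exposed it keeps C(4,2)·C(6,3) × C(2,1)·C(4,2) = 120 × 12 = 1440 of the 5040 allocations. If randomisation has been run, items 1 to 3 still apply, though a lopsided split will cost some precision.
5. Keep the exclusion analysis as a sensitivity analysis.

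The cost is a few lines in the Analysis plan and one or two floor-level degrees of freedom out of 16 floors.
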